### **3.3 STUDY ENDPOINTS**

#### **3.3.1 Primary Endpoint**

The proportion of participants who are successfully withdrawn from immunosuppression, which is defined as those who remain off immunosuppression for at least 1 year.

#### **3.3.2 Secondary Endpoints**

##### **3.3.2.1 Safety of Immunosuppression Withdrawal**

1. The proportion of participants who have graft loss or who die after initiation of immunosuppression withdrawal.
2. The time from the start of immunosuppression withdrawal to
  - a. the first episode of acute rejection requiring treatment,
  - b. the second episode of acute rejection not requiring treatment, or
  - c. the diagnosis of chronic rejection.
3. The distribution of histologic severity among rejection episodes.
4. The incidence of adverse events.
5. Changes in renal function, blood pressure, cholesterol level, and glucose control.

##### **3.3.2.2 Duration**

Immunosuppression-free duration, defined as the time from discontinuation of immunosuppression to end of trial participation or to time of restarting immunosuppression.

### **3.3.2.3 Tolerance Predictive Profiles**

Results of mechanistic studies and clinical assessments at various time points that allow for the definition of profiles associated with tolerance.

### **3.3.2.4 Rejection Profiles**

Results of mechanistic studies and clinical assessments that allow for definition of profiles associated with liver allograft rejection.

### **3.3.2.5 Assessment of Fibrosis Over Time for Participants Undergoing Extended Follow Up**

The change in periportal and pervedicular fibrosis on liver biopsy over time will be analyzed only for participants who remain off immunosuppression and enter Extended Participant Follow Up (see Appendix 4).

## **3.4 RATIONALE FOR SELECTION OF STUDY POPULATION**

The study population is defined in section 4.1. The proposed study aims to prospectively identify a cohort of stable patients who underwent parental living-donor liver transplantation when they were less than 18 years of age. This choice stems from the following:

- The concerning incidence of renal dysfunction, hypertension, and metabolic abnormalities related to long-term use of immunosuppressive medications in long-term (5–10 years) pediatric survivors of liver transplantation.
- The substantial potential benefit (physical, psychosocial, and financial) resulting from immunosuppressive withdrawal that participants can enjoy over a long lifetime.
- The availability of donor blood and recipient blood and tissue for mechanistic testing.
- The minimal maintenance immunosuppression currently utilized in these patients (a single agent) may increase the likelihood of successful withdrawal.

Patients for whom the indication for transplantation was hepatitis B, hepatitis C, autoimmune hepatitis, or primary sclerosing cholangitis are excluded because these diseases may recur after transplantation and their posttransplant course may be affected by withdrawal or intensification of immunosuppression as necessitated by a precipitated episode of rejection.

## **3.5 STOPPING RULES**

### **3.5.1 Ongoing Review**

The protocol chair, the ITN clinical trial physician, the NIAID medical monitor, and the NIAID Transplant Data and Safety Monitoring Board (DSMB) will periodically review safety data. Enrollment of participants in the trial and withdrawal of immunosuppression in current trial participants will be suspended at any time if any of these reviews concludes that there are significant safety concerns.

### **3.5.2 Specific Adverse Events Independent of Participant Enrollment**

Enrollment and immunosuppression withdrawal in trial participants will be suspended if any of the following occurs:

- Any death
- Any graft loss

- Two participants requiring antibody therapy for graft rejection
- Two participants diagnosed with chronic rejection

### 3.5.3 Specific Adverse Events as a Proportion of Enrolled Participants

An undue incidence of the following qualifying events will be grounds for suspending enrollment and immunosuppression withdrawal in trial participants:

- Severe graft rejection by Banff criteria.
- Rejection that requires more than one course of bolus corticosteroids.

Table 5 illustrates the thresholds for the number of qualifying events that would trigger suspension of enrollment and further withdrawal of immunosuppression in participants depending on the number of evaluable participants. The incidence rate is the number of participants with a qualifying event observed at any time after enrollment divided by the number of evaluable participants enrolled. An evaluable participant is defined as a participant who has been enrolled for at least 4 weeks or a participant who has had a qualifying event. These thresholds reflect the assumption that qualifying events should not occur in significantly more than 15% of participants in the trial. The basis for the stopping rule is that if there is reasonable evidence that the true event rate exceeds that value, suspension should occur. Each time a qualifying event occurs, the current number of evaluable participants can be compared with the number in Table 5 for the corresponding threshold. The trial will continue if the current number of evaluable participants for the threshold is greater than the number in Table 5 and will be suspended otherwise.

An 80% confidence interval is chosen, instead of a larger one, to reduce the chance of not suspending soon enough. Assessments begin with the second event.

**Table 5. Qualifying event thresholds triggering suspension of enrollment and immunosuppression withdrawal based on the number of evaluable participants**

Threshold for Number of Qualifying Events	Evaluable Participant Number	Observed Event Rate	80% Confidence Interval	
			Lower Bound	Upper Bound
2	3	0.67	0.20	0.97
3	7	0.43	0.17	0.72
4	11	0.36	0.17	0.60
5	16	0.31	0.16	0.50
6	20	0.30	0.17	0.47

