13. INTERIM ANALYSES AND DATA MONITORING

Per protocol version 4.0, there are not any planned interim analyses for this study.

The protocol chair, the ITN clinical trial physician, the NIAID medical monitor, and the NIAID Transplant Data and Safety Monitoring Board (DSMB) will periodically review safety data. Enrollment of subjects in the trial and withdrawal of immunosuppression in current trial subjects will be suspended at any time if any of these reviews concludes that there are significant safety concerns. Stopping rules are described in Section 3.5 of the protocol.

The progress of the study will be monitored by the NIAID Data and Safety Monitoring Board (NIAID DSMB). The NIAID transplant DSMB will be chartered to review safety data and to make recommendations regarding continuation, termination, or modification of the study. The DSMB will formally review the safety data at least yearly. The discontinuation of study treatment will also be periodically reported to the DSMB.

In addition, safety data will be reviewed by the DSMB when an event occurs that is of sufficient concern to the NIAID medical monitor or protocol co-chairs to warrant review, or when an event occurs that could contribute to a pre-defined stopping rule specified in the Protocol.

Findings will be reported to IRBs and health authorities.

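### Table 5's entries for 4 and 5 qualifying events (11 and 16) are each one participant below what the stated 15% rate and 80% interval give (12 and 17)

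*Protocol*

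**What the plan says.** Protocol section 3.5.3 covers two kinds of qualifying event: severe rejection by Banff criteria, and rejection needing more than one course of bolus corticosteroids. The reference rate is 15%: "These thresholds reflect the assumption that qualifying events should not occur in significantly more than 15% of participants in the trial". The principle is that "if there is reasonable evidence that the true event rate exceeds that value, suspension should occur". The level is explained: "An 80% confidence interval is chosen, instead of a larger one, to reduce the chance of not suspending soon enough".

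Table 5 is consulted at each qualifying event, from the second onward. "The trial will continue if the current number of evaluable participants for the threshold is greater than the number in Table 5"; otherwise it is suspended. For 2, 3, 4, 5 and 6 events the entries are 3, 7, 11, 16 and 20. Each row also gives the observed rate and the 80% limits.

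The section does not name the interval method, write the comparison as an inequality, or mention rounding. The SAP adds no detail; section 13 says only that "Stopping rules are described in Section 3.5 of the protocol".

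**The concern.** Because the trial continues only when the evaluable number is greater than the entry, each entry should be the largest number at which the evidence still calls for suspension. The natural way to combine a 15% reference, an 80% interval and reasonable evidence of a higher rate is to suspend when the lower 80% limit is above 0.15. On that reading the 4- and 5-event rows stop one participant too early.

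At 4 of 12 or 5 of 17, someone applying the text would suspend and someone applying the table would continue. The table gives the less cautious answer, although the protocol chose 80% over a larger level so as not to suspend too late.

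**Working it through.** **Inputs.** From Protocol 3.5.3: reference rate 0.15, two-sided 80% interval (10% in each tail), assessment from the second event, and the Table 5 entries. From the Synopsis: 20 participants, which caps the last row. The comparison (lower limit > 0.15) is inferred.

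**Step 1: reproduce the printed limits.** For x events in n participants the exact (Clopper-Pearson) limits are

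lower = 0.10 quantile of Beta(x, n − x + 1); upper = 0.90 quantile of Beta(x + 1, n − x).

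| x/n | Exact 80% limits | Table 5 |
|---|---|---|
| 2/3 | 0.1958 to 0.9655 | 0.20 to 0.97 |
| 3/7 | 0.1696 to 0.7214 | 0.17 to 0.72 |
| 4/11 | 0.1692 to 0.5995 | 0.17 to 0.60 |
| 5/16 | 0.1606 to 0.5035 | 0.16 to 0.50 |
| 6/20 | 0.1659 to 0.4673 | 0.17 to 0.47 |

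All ten limits match, so the printed figures are correct for the printed n. The continuity-corrected Wilson interval also rounds to all ten. Wald, Wilson, Jeffreys, Agresti-Coull and mid-P do not.

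**Step 2: find the largest n that still suspends.** The exact lower limit is above 0.15 exactly when P(X ≥ x | n, 0.15) is below 0.10.

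| x/n | Exact lower limit | P(X ≥ x) at 0.15 | Stated basis | Table 5 |
|---|---|---|---|---|
| 2/4 | 0.1426 | 0.1095 | continue | continue |
| 3/8 | 0.1469 | 0.1052 | continue | continue |
| 4/12 | 0.1542 | 0.0922 | suspend | continue |
| 4/13 | 0.1416 | 0.1180 | continue | continue |
| 5/17 | 0.1506 | 0.0987 | suspend | continue |
| 5/18 | 0.1418 | 0.1206 | continue | continue |

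The 6-event limit falls at n = 22 (0.15002), so the cap of 20 applies. The exact method therefore gives 3, 7, 12, 17, 20 against the printed 3, 7, 11, 16, 20. Continuity-corrected Wilson agrees on the two disputed rows (4/12 gives 0.1571, 5/17 gives 0.1529), although it gives 8 rather than 7 for 3 events.

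**Step 3: what would produce the printed entries.**
- *A higher level.* With unrounded exact limits, 4/12 continues only if the level is above 1 − 2(0.0922) = 81.6%, and 5/16 suspends only if it is below 1 − 2(0.0791) = 84.2%. All five printed entries therefore need a level between 81.6% and 84.2%.
- *Rounding.* Rounding the exact 80% lower limit to two decimals and requiring it to be strictly above 0.15 gives 3, 7, 11, 16, 21, which becomes the printed set after the cap of 20. Both 0.1542 and 0.1506 round to 0.15. This is the likely source.

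**Step 4: size.** The probability of ever suspending, with outcomes assessed one participant at a time from 1 to 20 (exact calculation):

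| True rate | Printed (11, 16) | Unrounded exact (12, 17) | Change, points |
|---|---|---|---|
| 15% | 16.6% | 18.1% | 1.5 |
| 20% | 33.0% | 35.3% | 2.3 |
| 30% | 69.4% | 71.6% | 2.2 |

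This ignores timing. A participant becomes evaluable after 4 weeks, so the denominator can fill before events occur. The documents give no timing for qualifying events, so event times were assumed lognormal (sigma 0.8) with a median of 10, 20 or 41 weeks, and accrual of two every 4 weeks or evenly over 2 years. In 40,000 simulated trials per case, the change was 0.0 to 1.3 points at a true 15% (at most 12.7% to 14.0%) and 0.0 to 1.8 points at 30% (at most 65.0% to 66.8%).

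**The case against.** The best defence is that no written rule is broken. Section 3.5.3 gives no inequality, method or rounding rule, and every printed row does have a lower limit above 0.15. One simple convention, exact limits at the two decimals the table prints, accounts for all five entries. At 5 of 17 the margin is only 0.0006. A different method that matches the printed limits would also change the 3-event row, so the documents do not fix the whole replacement table.

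The effect may also be close to nil. Protocol Table 3 reports a median time to rejection of 9.5 months, about 41 weeks, in the Kyoto cohort. With that median and two participants enrolled every 4 weeks, suspension probabilities did not change; with even accrual over 2 years they rose by 0.15 points at a true 15% and 0.25 points at 30%.

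There are backstops. Under section 3.5.1, enrollment and withdrawal "will be suspended at any time if any of these reviews concludes that there are significant safety concerns". Section 3.5.2 has absolute triggers such as "Two participants requiring antibody therapy for graft rejection". SAP section 13 also calls for board review "when an event occurs that could contribute to a pre-defined stopping rule specified in the Protocol", so neither disputed state would go unreviewed.

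Much of this stands: the comparison is inferred, the effect is small and the backstops are real. The rounding explanation shows how 11 and 16 probably arose, but it is written nowhere, and it moves the boundary against the protocol's own reason for choosing 80%. Both methods that match the printed limits give 12 and 17 when unrounded.

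**Conclusion.** The concern holds. The printed rates and limits are right, but the 4- and 5-event entries do not follow from the 15% and 80% basis: unrounded, it gives 12 and 17 where the table prints 11 and 16. Two assumptions carry this: that reasonable evidence means a lower 80% limit above 0.15, and that the limit is compared unrounded. The two affected states are 4 of 12 and 5 of 17.

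The consequence is small: 1.5 to 2.3 points in the chance of suspension in the one-at-a-time calculation, and 0 to 1.8 points under the assumed timing at true rates of 15% and 30%. It should still be fixed, because this is a safety boundary consulted at each qualifying event and the SAP relies on it without restating the rule.

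**What to change.** Reconcile Table 5 with its stated basis. Recompute the 4- and 5-event entries and their printed rates and limits from the unrounded lower limit; under the exact method the entries become 12 and 17 and the other three stand. Add a sentence to section 3.5.3 naming the interval method and the comparison with 0.15. If the sponsor intends a rounding convention instead, the section should state it and square it with the reason given for choosing 80%.

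The cost is two table rows and one sentence. The price of 12 and 17 is about 1.5 points more suspension when the true rate is exactly 15%, in the one-at-a-time calculation.

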### 3.6 PACE OF ENROLLMENT AND STUDY DURATION

Enrollment is defined as starting on the day that immunosuppression withdrawal is initiated. Enrollment is planned for 2 years and will be limited to a maximum of two participants every 4 weeks. Maximum patient participation is up to 11 years; therefore, the total study duration is projected to be a maximum of 13 years.

## 4. ELIGIBILITY

### 4.1 STUDY POPULATION

Pediatric recipients of parental living related donor hepatic allografts with adequate and stable graft function and no evidence of rejection or significant allograft dysfunction.

### 4.2 INCLUSION CRITERIA

1. Living-donor liver transplantation from a parental donor.
2. Age less than 18 years at the time of transplantation.
3. At least 4 years since transplantation.
4. Availability and willingness of parental liver donor to participate in the trial.
5. Liver biopsy at screening demonstrating no evidence of acute or chronic rejection and a less than stage 2 fibrosis on the Ishak scale.
6. Negative urine pregnancy test at entry and agreement to use a medically acceptable form of birth control during the study for women of childbearing potential.
7. Negative purified protein derivative (PPD) test results or history of appropriate treatment.

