### 4.3 EXCLUSION CRITERIA

1. Indication for transplantation liver failure due to autoimmune disease, such as autoimmune hepatitis, primary sclerosing cholangitis, or primary biliary cirrhosis.
2. Hepatitis B infection as defined by the presence of HBsAg or active treatment for hepatitis B.
3. Hepatitis C infection as defined by the presence of antibody against hepatitis C.
4. Serologic evidence of autoimmunity defined as abnormal antinuclear, anti-smooth-muscle, antimitochondrial, or anti-liver-kidney microsomal antibody titers greater than or equal to 1:160.
5. Transplantation of a second organ before, simultaneously with, or after liver transplantation; or liver retransplantation.
6. Aspartate or alanine aminotransferase (AST or ALT) greater than 2 times the upper limit of normal.
7. Total bilirubin and direct bilirubin, and either alkaline phosphatase or gamma-glutamyl transferase (GGT) greater than 2 times the upper limit of normal.
8. Clinically significant change in hepatic function in the past 26 weeks.
9. GFR less than 40 mL/min/1.73 m^2.
10. Immunosuppression with
  - a. a 50% dose increase in a current agent within 26 weeks of screening, *or*
  - b. more than one agent within 52 weeks of screening.
11. Any systemic illness requiring or likely to require immunosuppressive drug use.

12. Human immunodeficiency virus (HIV) infection.
13. Pregnancy or breastfeeding.
14. Unwillingness or inability to comply with study requirements and procedures.

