## 6. STUDY PROCEDURES

### 6.1 VISIT WINDOWS

All visits, except as noted below, should be completed within  $\pm 2$  weeks of the scheduled time points in the SOE (see Appendices 1–4):

- Screening
  - Interval between visits  $-2$  and  $-1$  will not exceed 9 weeks.
  - Interval between visits  $-1$  and  $0$  will not exceed 2 weeks.
- Initiation or interruption of gradual withdrawal of immunosuppression
  - Immunosuppression withdrawal (visit  $0$ ) may begin on the same day as the liver biopsy (visit  $-1$ ) or up to 2 weeks afterwards.
  - Additional monitoring at the current immunosuppression dose level may be indicated before continuing with the gradual withdrawal of immunosuppression. If so, the maximum interruption period may not exceed 4 weeks (see section 5.1).
- Liver biopsies
  - A liver biopsy to determine eligibility at screening (visit  $-1$ ) may be performed no later than 9 weeks after the initial screening visit (visit  $-2$ ).
  - If a for-cause biopsy is performed within 6 weeks of a scheduled study visit that includes a protocol biopsy, then all the tests (including ITN Core Laboratory blood draws, clinical assessments, etc.) for the scheduled visit can be conducted at the time as the for-cause biopsy.
  - For participants who have successfully withdrawn from immunosuppression, a biopsy will be performed within 4 to 8 weeks after the last dose of immunosuppressant was taken. In order for the biopsy to be performed within this time period, the window for the visit on which this biopsy occurs will be extended to  $\pm 6$  weeks.

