5. ANALYSIS POPULATIONS

Intent to treat (ITT) sample will be defined as all subjects who have signed informed consent and are enrolled. For the purpose of these analyses enrollment is defined as beginning the screening process for participation in the study.

Per protocol (PP) samples will be defined as all subjects in whom immunosuppression withdrawal is attempted.

- Per protocol 1 (PP1) sample will be defined as all subjects in whom immunosuppression withdrawal is attempted.
- Per protocol 2 (PP2) sample will be defined as all subjects without inclusion/exclusion criteria protocol deviations in whom immunosuppression withdrawal is attempted.

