9.1.3 Assessment Time Windows

All visits, except as noted below, should be completed within ± 2 weeks of the scheduled time points in the Schedule of Events.

-Screening

- Interval between visits -2 and -1 will not exceed 9 weeks.
- Interval between visits -1 and 0 will not exceed 2 weeks.

-Initiation or interruption of gradual withdrawal of immunosuppression

- Immunosuppression withdrawal (visit 0) may begin on the same day as the liver biopsy

(visit -1) or up to 2 weeks afterwards.

- Additional monitoring at the current immunosuppression dose level may be indicated before continuing with the gradual withdrawal of immunosuppression. If so, the maximum interruption period may not exceed 4 weeks (see section 5.1).

- Liver biopsies

- A liver biopsy to determine eligibility at screening (visit -1) may be performed no later than 9 weeks after the initial screening visit (visit -2).
- If a for-cause biopsy is performed within 6 weeks of a scheduled study visit that includes a protocol biopsy, then all the tests (including ITN Core Laboratory blood draws, clinical assessments, etc.) for the scheduled visit can be conducted at the time as the for-cause biopsy.
- For subjects who have successfully withdrawn from immunosuppression, a biopsy will be performed within 4 to 8 weeks after the last dose of immunosuppressant was taken. In order for the biopsy to be performed within this time period, the window for the visit on which this biopsy occurs will be extended to ± 6 weeks.

Unscheduled visits may also occur throughout the study.

Measurements from unscheduled visits, scheduled visits obtained outside the scheduled assessment time windows, and windowed measurements not closest to the scheduled target day will be included in listings only and not in by-visit tabular displays.

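### The only scheduled pregnancy test is at visit -2, up to 9 weeks before the biopsy and eligibility review and up to 11 weeks before enrollment, so the schedule does not verify pregnancy status at either point

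*Protocol*

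**What the plan says.** Protocol 4.2, item 6, requires, for women of childbearing potential, a "Negative urine pregnancy test at entry and agreement to use a medically acceptable form of birth control during the study". The synopsis carries the same requirement. Protocol 4.3, item 13, lists "Pregnancy or breastfeeding" as an exclusion. No section says what 'entry' means.

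Protocol 3.6 defines a different word: "Enrollment is defined as starting on the day that immunosuppression withdrawal is initiated". That day is visit 0. Protocol 3.2 has people screened first, then enrolled once they meet the criteria. SAP section 5 uses another meaning: "For the purpose of these analyses enrollment is defined as beginning the screening process for participation in the study".

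The urine hCG row of Appendix 1 has a single mark, at visit -2, in the protocol and again in SAP 16.1. The inclusion/exclusion review and the screening biopsy are marked at visit -1. Protocol 6.3 lists urine hCG among the local tests without a time.

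On the intervals, Protocol 6.1 says that the screening biopsy "may be performed no later than 9 weeks after the initial screening visit", and that withdrawal may begin on the biopsy day "or up to 2 weeks afterwards". SAP 9.1.3 agrees: "Interval between visits -2 and -1 will not exceed 9 weeks" and "Interval between visits -1 and 0 will not exceed 2 weeks".

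**The concern.** Two eligibility criteria turn on pregnancy status, but the one test that informs them is placed at the first screening visit, and the windows let that visit fall well before the decisions it supports. The investigator can sign off inclusion 6 and exclusion 13 at visit -1 on a result from weeks before. A participant who conceived after visit -2 would still have a negative test on file when she has the percutaneous biopsy and when withdrawal starts.

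The case is not hypothetical for this population. The age limit in Protocol 4.2 applies at transplantation, not at enrollment, and Protocol 3.2 has a consent category for participants aged 18 and over. Inclusion 6 itself presupposes participants of childbearing potential.

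What is at stake is participant safety and the ability to show that each enrolled participant was eligible.

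**Working it through.** The documents state no figure to reproduce. The check is to read the schedule and add the permitted intervals.

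**1. How many tests, and when?**
- Appendix 1 has one urine hCG mark, in the visit -2 column. The column can be trusted despite the broken table: rows marked first at visit -1, such as drug levels and the eligibility review, carry an extra empty cell, and the hCG row does not.
- SAP 16.1, Appendix 1, is identical.
- Protocol Appendices 2 to 4 and SAP Appendices 2 and 3 have no urine hCG row, so no later scheduled test would pick up a missed pregnancy.
- Footnotes 1 and 8 of Appendix 1 give timing or deferral options for other samples. Neither is attached to urine hCG.

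**2. How old can the result be?**

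| Interval | Source | Maximum |
|---|---|---|
| Visit -2 to visit -1 (biopsy, eligibility review) | Protocol 6.1; SAP 9.1.3 | 9 weeks |
| Visit -1 to visit 0 (withdrawal starts) | Protocol 6.1; SAP 9.1.3 | 2 weeks |

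- Test to biopsy and eligibility review: at most 9 weeks = 9 × 7 = 63 days.
- Test to enrollment: at most 9 + 2 = 11 weeks = 11 × 7 = 77 days.

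The general window of ±2 weeks does not lengthen these, because the screening intervals are listed as exceptions to it. No minimum interval is set, and visits -1 and 0 may be the same day, so actual gaps may be much shorter.

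**3. Which meaning of 'entry' fits the text?**
- *Entry as enrollment (visit 0).* The visit -2 test can be up to 11 weeks early. The wording leans this way: inclusion 5, directly above, places the liver biopsy at screening, exclusion 10 counts back from screening, and Protocol 6.2 places the PPD test at screening. The authors used that word when they meant it and chose another for item 6.
- *Entry as the start of screening (visit -2).* Inclusion 6 is then met by the scheduled test. Exclusion 13 still has no test behind it at the biopsy or at enrollment.

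On either reading the schedule does not verify status at visit -1 or visit 0.

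**4. Does it move any statistical result?**
SAP section 5 removes participants with inclusion/exclusion deviations from PP2 and keeps them in PP1. As an illustration, take the plan's own example of 9 successes in 20 (45%) and remove one participant:
- if she was a success: 8/19 = 42.1%, a shift of 42.1 − 45.0 = −2.9 points;
- if she was a failure: 9/19 = 47.4%, a shift of 47.4 − 45.0 = +2.4 points.

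The plan's exact 95% interval for 9/20 runs from 23.1% to 68.5%. A shift of this size in a secondary sample is immaterial, and the PP1 result does not change.

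**The case against.** The strongest objection is that 'entry' is undefined. Protocol 3.6 defines enrollment, and inclusion 6 does not use that word. The SAP equates enrollment with the start of screening, and on that sense the visit -2 test meets inclusion 6. This stands to the extent that a breach of inclusion 6 cannot be called proven. It does not dispose of the point: the SAP limits its definition to its own analyses, the protocol's wording leans the other way, and exclusion 13 remains untested at visits -1 and 0 in any case.

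Second, there are other safeguards. Exclusion 13 applies whatever the date of the test; eligibility is reviewed at visit -1; participants agree to use birth control; the biopsy has its own consent; and Protocol 8.5.4 requires a pregnancy to be reported within 24 hours and followed to its conclusion. These reduce the risk, and it would be wrong to write as if nothing stood between visits -2 and 0. None of them establishes pregnancy status, and the protocol itself asks for a test in addition to the agreement on birth control.

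Third, a test at visit -1 would still precede enrollment by up to 2 weeks. That is true, so such a move narrows the gap without closing it unless 'entry' is defined to match.

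A reader might also draw two stronger conclusions that the documents do not support. One is that any pregnancy discovered after enrollment is an eligibility deviation. It is one only if the pregnancy already existed at enrollment; conception afterwards breaches no entry criterion and leaves PP2 unchanged. The other is that, because one participant is 1/20 = 5 percentage points, the primary result is at risk by that amount. That is a participant's share of the denominator, not an effect of pregnancy on the endpoint.

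**Conclusion.** The point holds as a mismatch between the eligibility criteria and the schedule. The single scheduled test can be up to 9 weeks old at the biopsy and eligibility review and up to 11 weeks old at enrollment, so the schedule does not verify pregnancy status at either point.

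The 9 weeks rests only on the visit windows. The 11 weeks also uses the Protocol 3.6 definition of enrollment. Neither depends on how 'entry' is read. Whether inclusion 6 itself is unmet does depend on that reading, and the documents leave it open while leaning towards a time later than the start of screening.

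The number of participants affected cannot be derived from the documents and is probably small. The sponsor should correct this on grounds of eligibility verification and safety; no statistical figure is materially affected.

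**What to change.** Define 'entry' in inclusion 6 and align the urine hCG mark with that definition, so that Protocol 4.2 (item 6), 4.3 (item 13), 3.6, 6.1 and Appendix 1, and SAP 16.1 Appendix 1, agree. Which time point to adopt is for the sponsor and investigators.

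One option that fits the existing schedule is to place the test at visit -1 before the biopsy, where the criteria are already reviewed, and to define 'entry' as that test. The result would then precede the biopsy at the same visit, and the maximum gap to enrollment would fall from 11 weeks to 2.

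The cost is one cell in two schedules, a line of definition, and ethics approval of the amendment before use (Protocol 12.1). It needs no extra visit and, if the mark is moved, no extra test. The small downside of moving it without repeating it is that a pregnancy already present at visit -2 is found later in screening, by up to 9 weeks. Keeping the visit -2 test and adding a second would avoid that for the price of one more urine test.
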